Increased physical activity (PA) is consistently associated with fewer treatment-related side effects, higher QOL, increased survival and reduced recurrence and mortality⁶⁻⁹ among early stage survivors. Increasing light intensity PA and reducing time spent sedentary may also reduce functional decline,¹⁰ improve QOL and QOL^{11, 12} and body composition¹³ and reduced mortality¹⁴ independent of more intense PA. However, there is a paucity of research on PA in MBC patients. Two out of the three existing interventions in MBC patients^{15, 16} were deemed not feasible due to their focus on intense PA and/or requiring on-site visits. Thus, PA interventions which use mobile health (mHealth) technology may be particularly useful for these women because they allow for remote monitoring of patients which facilitates individual tailoring of PA programs to patient's abilities and do not require travel to on-site, supervised PA sessions, reducing participant burden. However, no studies have examined effects of a mHealth intervention on PA in MBC patients. The proposed study seeks to address these critical research gaps by testing a highly tailored, remotely delivered mHealth intervention to promote PA of any intensity (i.e. light, moderate or vigorous) via increasing daily steps in MBC patients. This approach may have substantial health benefits for MBC patients, facilitate gradual and safe adoption of more intense PA and be more achievable than high volumes of more strenuous PA.^{17, 18}

The primary purpose of the present study is to pilot test the feasibility and acceptability of a 12 week remotely delivered mHealth intervention to increase PA in MBC patients using a two-arm randomized control trial (RCT). We will also examine the effects of the intervention on symptom burden, QOL and functional performance, important outcomes in MBC patients. Inactive MBC patients (n=50) will be assigned to *Fit2ThriveMB* or education control. Participants assigned to the *Fit2ThriveMB* will receive the *Fit2ThriveMB* smartphone app, Fitbit, and coaching calls. Participants in the education control will receive educational materials and calls during the intervention period and the Fitbit following completion of 12 week assessments. The proposed study represents the first systematic effort to test a mHealth intervention to increase PA in MBC patients. This study addresses a critical research question related to PA and cancer survivorship (i.e. Is there a role for PA in advanced cancer?)¹⁹ and supports NCI's research priorities of creating more feasible mHealth PA interventions for survivors.¹¹ Findings from this study will provide essential knowledge to help understand the health benefits of increasing PA in MBC patients. Specific aims are:

Aim 1. To pilot test the feasibility and acceptability of *Fit2ThriveMB*, a 12-week mHealth PA intervention in MBC patients (n=50) in a two-arm RCT (*Fit2ThriveMB* vs. education control). We hypothesize the following: a) $\geq 80\%$ of MBC patients will be retained in the intervention; b) enrollees will set an individualized PA goal, adhere to their goals and wear the Fitbit on $\geq 70\%$ of study days and c) $\geq 70\%$ of participants will rate the intervention as acceptable.

Aim 2. To examine the potential effects of *Fit2ThriveMB* on PA. MBC patients in *Fit2ThriveMB* will demonstrate greater increases in PA as measured by average daily accelerometer-assessed steps and time spent in any activity intensity (light, moderate or vigorous) than education controls at 12 weeks.

Aim 3. To examine outcome patterns suggesting the efficacy of *Fit2ThriveMB* for improving symptom burden (i.e. fatigue, depression, anxiety, pain, and physical function), functional performance and QOL

compared to education control. MBC patients in *Fit2ThriveMB* will demonstrate more favorable symptom profiles, functional performance and QOL than controls at 12 weeks as measured by well-validated standardized measures.

The proposed study is the first to test the effects of a mHealth intervention to increase PA in MBC patients. The proposed study will inform a fully-powered R01 by providing insight into: a) feasibility and acceptability of *Fit2ThriveMB* and b) preliminary effect sizes for PA, symptom burden, functional performance and QOL. Ultimately, the proposed study will provide key evidence to support the feasibility, acceptability and health benefits of increasing PA in MBC patients using a scalable intervention strategy that could be easily integrated into care to improve health and disease outcomes.

2.0 Background / Literature Review / Rationale for the study:

Increased incidence and life expectancy has resulted in a growing population of metastatic breast cancer (MBC) patients.¹ MBC patients have poorer quality of life (QOL) and higher rates of functional decline and premature mortality compared to early stage survivors and healthy controls.²⁻⁴ Interventions are needed to alleviate adverse health effects and allow metastatic patients to function optimally in the years they survive with advanced cancer. However, few health-enhancing interventions exist for women with MBC. Increased physical activity (PA) is consistently associated with fewer treatment-related side effects, higher QOL, increased survival and reduced recurrence and mortality among early stage survivors.⁶⁻⁹ Increasing light intensity PA and reducing time spent sedentary may also reduce functional decline,¹⁰ improve QOL and QOL^{11, 12} and body composition¹³ and reduced mortality¹⁴ independent of more intense PA. However, there is a paucity of research on PA in MBC patients, and existing interventions have been deemed not feasible due to their focus on intense PA and/or requiring on-site visits. mHealth PA interventions may be particularly useful for these women because they allow for remote monitoring of patients which facilitates individual tailoring of PA programs to patient's abilities and do not require travel to on-site, supervised PA sessions, reducing participant burden. Yet, no studies have examined a mHealth PA intervention in MBC patients. We propose to address these critical research gaps by testing a highly tailored technology-supported intervention to promote PA of any intensity (i.e. light, moderate or vigorous) via increasing daily steps in MBC patients. This approach may have substantial health benefits for MBC patients, facilitate gradual and safe adoption of more intense PA and be more achievable than high volumes of more strenuous PA.^{17, 18} The primary aim of this study is to pilot test the feasibility and acceptability of a 12 week technology-supported intervention to increase PA in inactive MBC patients (n=50) using a two-arm randomized control trial (*Fit2ThriveMB* versus education control). The *Fit2ThriveMB* intervention consists of a Fitbit, coaching calls and the *Fit2ThriveMB* smartphone app which provides self-monitoring, a tailored goal-setting tool, real-time tailored feedback, app notifications, and a group message board. We will also examine outcome patterns suggesting the efficacy of *Fit2ThriveMB* on symptom burden, QOL and functional performance, important outcomes in MBC patients compared to the education control. The primary outcome time point is post-intervention 12 weeks. This project is significant because it will provide essential evidence to support the feasibility, acceptability and health benefits of increasing PA in MBC patients using a scalable intervention strategy that could be easily integrated into care to improve health and disease outcomes in this population.

3.0 Inclusion and Exclusion Criteria:

Inclusion criteria:

- Female; ≥ 18 years of age
- Diagnosed with metastatic breast cancer or locally advanced disease not amenable to surgical resection (Metastases to the auxiliary lymph nodes, and nowhere else in the body, do not qualify).
- Fluent in spoken and written English
- Own a smartphone
- Have access to the internet to complete assessments

- Self-report engaging in <150 minutes of moderate to vigorous PA per week.

Exclusion criteria:

- Untreated brain metastases
- Breast cancer with metastases to only the auxiliary lymph nodes.
- Uncontrolled cardiovascular disease or other major contraindications (i.e. non-ambulatory, severe cognitive or functional limitations) to PA participation
- Current enrollment in another dietary or PA trial

All MBC patients must obtain medical clearance from their oncologist to participate.

Adults unable to consent/Cognitively Impaired, individuals who are not yet adults (under 18 years of age), pregnant women and prisoners or other detained individuals will NOT be included in the present study.

4.0 Sample Size:

We will recruit 50 metastatic breast cancer patients to participate in this study. Sample size calculations (n=50) are based on the successful completion rate defined as: a) an attrition rate of $\leq 20\%$ (i.e. complete 12 week assessment) and b) adherence to daily goals and wearing Fitbit $\geq 70\%$ of study days (i.e. $\sim 59/84$ days). With half of participants (n=25) assigned to each condition, there is $>85\%$ power to differentiate between a 60% (control) and 80% (*Fit2ThriveMB*) “successful completion” rate with a one-tailed, exact test for binomial proportion at a 0.05 significance level (SAS V9.4).

5.0 Recruitment and Screening Methods:

Participants will be recruited from the following sites, all affiliated with Northwestern University Feinberg School of Medicine and the Lurie Comprehensive Cancer Center, or additional Northwestern Medicine sites : a) outpatient facility at Galter Pavilion of Northwestern Memorial Hospital; b) Lynn Sage Comprehensive Breast Cancer Center at Prentice Women’s Hospital; and c) additional Northwestern Medicine Cancer Center locations (e.g. Cancer Center at Northwestern Medicine Lake Forest Hospital, Northwestern Medicine McHenry Hospital Cancer Center, Northwestern Medicine Cancer Center Delnor). For all methods, we will consult with patient’s oncologists on an as needed basis to help determine if potential patients are good potential candidates for participation.

Screening

Participants will complete initial eligibility screening online or over the phone. It will take approximately 15 minutes. Screening will include evaluation of eligibility, the Physical Activity Readiness Questionnaire (PAR-Q)²⁰, which assesses cardiovascular disease history, symptoms, risk factors, and other health issues and the Fall Risk Assessment Questionnaire (FRQ)²¹, which identifies individuals who may be at risk for falling. Screening will also include questions regarding technology and equipment the women currently have at home that may be usable for the baseline and week 12 functional performance video conference assessments. All women will also be required to obtain medical clearance from their oncologist.

Method 1: Recruitment Emails. The Northwestern Enterprise Data Warehouse (NMEDW) NMEDW (<https://www.nucats.northwestern.edu/resources/data-science-and-informatics/nmedw/index.html>) was designed to create a single, comprehensive and integrated repository of all clinical and research data sources on the campus to facilitate research, clinical quality, healthcare operations and medical education. We will use the NMEDW to obtain lists of NU patients who have agreed to be contacted regarding research study opportunities at Northwestern University and meet gross eligibility criteria with respect to diagnosis. We have also obtained an exception to view the clinic schedule in EPIC to compliment the NMEDW list. Patients who have come in for a visit recently, who meet the eligibility requirements, will be identified through this schedule. In addition, we have been granted access to oncologist’s schedules via the exception process. Potential participants recruited through the NMEDW or clinic schedules will be e-mailed a letter notifying them about the study. This email will also contain a link to complete the

online screening housed in REDCap if they are interested in participating. If an individual does not want to participate, they will be asked to simply indicate this by responding to the e-mail. If we do not hear from the patient within 3-5 business days, we will follow-up with additional phone or email contacts, but will not exceed three attempts. If at least 6 months pass following the initial recruitment attempt with no response from the patient, an additional, single recruitment attempt may be made via phone call and/or email.

Method 2: Physician Referral. Clinicians will be encouraged to discuss the study with their patients. If her physician discusses the study with her and she agrees to have them send study staff her name, we will either e-mail her a description of the study and a link to complete the on-line screening, or follow-up with a phone call. If we do not hear from the patient within 3-5 business days, we will follow-up with additional contacts via telephone call or e-mail, but will not exceed 3 attempts.

Method 3: Self-Referral. If an individual contacts the researcher and is interested in participating in the study, s/he will be screened over the phone or online. The Study Coordinator will also work with the clinical team to confirm eligibility and appropriateness for the study. Subjects may self-refer to the study after hearing about it via clinic flyers, word of mouth, or via the media/NU newsletters if the principal investigator is interviewed.

6.0 Research Locations:

Research procedures will take place in the Department of Preventive Medicine at Northwestern University Feinberg School of Medicine.

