Those who are eligible, agree to participate, provide informed consent, and provide physician consent will be: a) scheduled for a functional performance testing video conference with study staff via Zoom; b) sent an email with an individual, secure link to study questionnaires via REDCap and c) notified an accelerometer has been mailed. Participants will be asked to complete questionnaires within 1 week of receipt. MBC patients will be provided with detailed written instructions for wearing the accelerometer and directed to wear the monitor on specified dates attached to on the non-dominant hip during all waking hours, except when bathing or swimming, for 7 consecutive days and return the monitor and monitor log to the study team through the mail using a postage paid envelope provided by the study team. The questionnaires will take approximately 30-45 minutes to complete. The functional performance video conference will consist of completion of remote, individual functional performance testing (see Measures). In addition to the accelerometer and accelerometer instructions, participants will be mailed a remote functional performance testing kit that will include equipment required to complete the testing (i.e. blood pressure cuff, pedometer, hand weight, rope pre-measured for test distances, digital scale). The functional performance testing video conference will last from 60-90 minutes. Procedures will be the same at baseline and 12 weeks. Participants will be asked to hold onto the functional performance testing kit for the 12 week study so materials can be used at baseline and 12 weeks and will be provided with a postage paid box to ship materials back to the study team at week 12. At 12 weeks, the control group will participate in a virtual functional performance testing session and an optional virtual brief orientation to the app and Fitbit . The intervention group will participate in video conference functional performance testing and a study information and feedback session, which may occur via group video conference, or an individual phone call or video conference. Participants in the intervention group will also be provided with instructions for how to delete the Fit2ThriveMB app at the conclusion of the 12-week intervention. In addition, all participants will be asked to complete a short questionnaire battery during week 3 that will take approximately 10-15 minutes to complete.

Randomization and Orientation

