After remote functional performance testing is complete, assessment materials (i.e. accelerometer, activity wear log, etc.) are received in the mail by study staff, and all data are verified, MBC patients (n=50) will be randomized 1:1 to *Fit2ThriveMB* intervention or education control group using computer-generated randomly permuted blocks. Individuals randomized to the *Fit2ThriveMB* intervention group will receive all intervention materials in the mail, and will participate in a remote, group or individual (depending on scheduling conflicts) orientation via Zoom video conference which will consist of instructions on all intervention procedures and assistance with downloading and setting up the *Fit2ThriveMB* app, Fitbit and Fitbit app. MBC patients assigned to the education control will also receive all control group materials via mail and will participate in a remote, group or individual (depending on scheduling conflicts) orientation session via Zoom video conference, during which they will receive instructions on study procedures and assistance with downloading and setting up the Cancer.Net app. Individuals in the control group will be informed they will receive the Fitbit after completion of 12 week assessments. The study orientation video conferences will take approximately 60-90 minutes. As in our previous studies, participants will start the intervention in cohorts of 6-12 individuals per condition to ensure an adequate number of participants for the *Fit2ThriveMB* message board.

Intervention Components

Fit2ThriveMB Intervention

The *Fit2ThriveMB* intervention will consist of the Fitbit, *Fit2ThriveMB* app, and weekly coaching calls that will last from 10-15 minutes each. **Table 1** provides an overview of the weekly schedule of content for the intervention.

Table 1. *Fit2ThriveMB* Weekly Schedule of Intervention Content

| Week | Theme | Daily Goal Setting | Daily Symptom Report | Tailored Push Notifications | Weekly Coaching Call |
|------|---|--------------------|----------------------|-----------------------------|----------------------|
| 1 | Intro to coaching calls/Getting started/SMART Goals | Yes | Yes | 2-3/day | Yes |

| | | | | | |
|----|--|-----|-----|---------|-----|
| 2 | Benefits Reducing Sitting and Overcoming Barriers to Reducing Sedentary Behavior | Yes | Yes | 2-3/day | Yes |
| 3 | Benefits of Increasing PA and increasing steps | Yes | Yes | 2-3/day | Yes |
| 4 | Finding Activities You Enjoy | Yes | Yes | 2-3/day | Yes |

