At the end of the 12 week intervention, participants in the education control group will receive a Fitbit and have access to the *Fit2ThriveMB* study app. If they choose to download the app and use it, the app will collect data including: login frequency, app usage, data entered into the app including symptom burden, goal selection and physical activity and data transmitted from the Fitbit, including physical activity and steps taken. This data will be collected for 12 months and stored for the purpose of analyzing post-intervention app usage and physical activity patterns. At the end of 12 months the app will no longer function. Participants will be instructed in how to download, and provided with written instructions for removing the app, if they wish following the 12 week assessment. Once the app is removed we will be unable to collect any data from their phone.

Support Calls

To match *Fit2ThriveMB* contacts, participants will also receive weekly calls that will cover health and well-being topics (see Table 3). They will be provided with the Fitbit after completion of week 12 assessments.

Table 3: Healthy Living Control Coaching Call Content

| Week | Theme |
|------|--|
| 1 | Mindfulness |
| 2 | Social Support: Friends, Family, Counseling and Support Groups |
| 3 | Social Support: Online Communities |
| 4 | Symptom Tracking |

| | |
|----|---|
| 5 | Art Therapy/Doing Activities you Enjoy (focus on quality of life) |
| 6 | Sleep |
| 7 | Fatigue |
| 8 | Cognition |
| 9 | Hydration |
| 10 | Nutrition |
| 11 | Healthy Grocery Shopping |
| 12 | Stress Management |

Study Retention Plan

To minimize attrition, study staff will develop good rapport with participants during recruitment and maintain the relationship throughout the study (e.g., by sending birthday cards). Participants will be provided with a phone number to call immediately if they encounter issues with any aspect of the intervention. Staff will convey reminders of scheduled assessments by phone, email, or text message, per participant preference. Participants will also be incentivized to complete assessments (\$41.50 at baseline and 12 weeks) for a total of \$83.00. Participants will be paid \$40.00 for completing the assessments in their entirety, and will be paid an additional \$1.50 at each time point to cover the cost of transferring the electronic payment to a personal checking account, if the participant chooses. Also, participants will receive a free Fitbit.

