Feasibility will primarily be assessed via: a) participant retention (# of participants who drop out/ # randomized) and b) intervention adherence (% days adhere to daily goal and % of days wear Fitbit). The Fitbit is sufficiently well-validated for steps to support its role as an adherence measure in this study.

Adherence

Adherence during the 12 week intervention will be monitored continuously using Fit2ThriveMB app. As in our ongoing Fit2Thrive trial, we will obtain tracker wear time, steps, and time spent in sedentary, light, moderate, and vigorous intensity activity. Acceptability will be measured via a process evaluation of perceptions of MBC patients' experiences with Fit2ThriveMB.

Secondary Outcomes

Physical Activity and Sedentary Behavior

Actigraph Accelerometer: The ActiGraph accelerometer (model wGT3X- BT, ActiGraph, Pensacola, FL), a well-validated and reliable measure of objective PA^{22, 23} will be used. It is blinded to the participant (i.e., no display or feedback). At each time point, participants will wear the device for 7 consecutive days during all waking hours, except when bathing or swimming. Participants will be instructed on how to wear the device and will use a log to record wear time and note any deviations from the wear protocol. After each wear period, data will be downloaded and screened for completeness and irregularities. Participants will be asked to re-wear the ActiGraph if it was not worn for at least 10 hrs/day for ≥ 5 days. Sixty consecutive zeros will be designated as non-wear time. Data will be collected in one-minute intervals (epochs). Each valid minute of wear time will be classified according to intensity (counts/min) using commonly accepted cut-points: sedentary (<100), light activity (100-2019) and MVPA (≥ 2020).^{24, 25}

Sitting Time Questionnaire.²⁶ Women will be asked to indicate the amount of time they spend on a typical weekday and weekend sitting in the following activities: traveling to and from places, while at work, while watching television, while using a computer at home in leisure time NOT including television (e.g. visiting friends, movies, dining out, etc.). Test-retest reliability coefficients were high for weekday sitting time at work, watching television and using a computer at home ($r_s=0.78-0.84$) but are more variable for weekend days across all domains ($r_s=0.23-0.74$).

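### The stated power above 85% is not delivered with 25 women per arm (exact power is 62–73% one-sample, 35–44% two-sample), and the control comparison cannot be made on the composite outcome

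*Combined protocol and SAP*

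**What the plan says.** Section 4.0 opens its justification with "Sample size calculations (n=50) are based on the successful completion rate defined as" two parts: (a) attrition of at most 20%, judged by completing the 12-week assessment, and (b) adherence to daily goals and Fitbit wear on at least 70% of study days, about 59 of 84. With 25 women in each condition it then claims more than 85% "power to differentiate between a 60% (control) and 80"% (Fit2ThriveMB) on this "rate with a one-tailed, exact test for binomial proportion at a 0.05 significance level (SAS V9.4").

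Section 9.0 describes how the parts are measured. Under Measures, feasibility includes "intervention adherence (% days adhere to daily goal and % of days wear Fitbit"), and "Adherence during the 12 week intervention will be monitored continuously using Fit2ThriveMB app". On the control arm, Randomization and Orientation says: "Individuals in the control group will be informed they will receive the Fitbit after completion of 12 week assessments". The Education Control text agrees: "At the end of the 12 week intervention, participants in the education control group will receive a Fitbit and have access to the" study app. That text also tells controls to carry on with their usual activities.

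The Statistical Analyses Plan for Aim 1 uses frequencies, means and standard deviations. It frames successful completion around women who enrol in the intervention and contains no test against control.

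**The concern.** Section 4.0 gives every input needed to check its power figure, and 25 per arm looks too few to separate 60% from 80% with power above 85% by any exact test. The wording also mixes two designs: the test named is a one-sample test for a proportion, but the rates are labelled as belonging to two randomised arms.

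There is a second problem. Part (b) of the composite needs a Fitbit and daily step goals, and controls have neither from the study until week 12 is over. A control rate on the composite would have no data behind it.

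This is the only quantitative justification for n=50, it concerns the primary outcome, and the pilot is meant to inform a fully powered trial. A reader would conclude that a true 80% against 60% is missed less than 15% of the time.

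**Working it through.** **Inputs, all from section 4.0.** 25 women per condition (50 in total); rates 0.60 (control) and 0.80 (Fit2ThriveMB); one-tailed exact test; alpha 0.05; stated power above 85%.

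**1. One-sample exact test, n=25, null 0.60.** Find the smallest r with P(X ≥ r | 25, 0.60) ≤ 0.05; power is P(X ≥ r | 25, 0.80).
- r = 19: alpha 0.074, too large. Even this inadmissible cut-off would give power of only 0.780.
- r = 20: alpha 0.029, admissible. **Power 0.617.**
- With r = 20, power reaches 0.85 only at a true rate of 0.853.

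**2. Same test with the null at 0.80 and a true rate of 0.60.** Reject at X ≤ 16: P(X ≤ 16 | 25, 0.80) = 0.047 and P(X ≤ 16 | 25, 0.60) = 0.726. **Power 0.726.**

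**3. Two-sample exact tests, 25 v 25, one-sided 0.05.** Power is the sum of Bin(x; 25, 0.60) × Bin(y; 25, 0.80) over all pairs (x, y) that the test rejects.
- Fisher: **0.351**
- Exact unconditional, pooled-z ordering: 0.435 (size 0.044)
- Boschloo: **0.443** (size 0.047)

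**4. Attempts to reproduce the stated figure.**

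| Variant (one-sided) | Power |
|---|---|
| 25 v 25, mid-p | 0.446 |
| 25 v 25, normal approximation | 0.458 |
| 25 v 25, chi-square | 0.463 |
| One-sample n=25, normal approximation | 0.686 |
| One-sample n=25, normal, alternative variance only | 0.804 |
| 50 v 50, Fisher to chi-square | 0.636 to 0.720 |
| One-sample exact n=50, null 0.60 (reject at ≥ 37, alpha 0.028) | **0.889** |
| One-sample exact n=50, null 0.80 (reject at ≤ 34, alpha 0.031) | 0.904 |

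No variant with 25 per arm reaches 0.85. A one-sample test on all 50 women does.

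**5. Sample size that would support the claim.** One-sample exact power against 0.60 first passes 0.85 at n=39 (0.859). It falls below again at n=40, 41 and 44 (0.839, 0.818, 0.846), and stays above from n=45 (0.901) at every n checked up to 60. A one-sided two-sample comparison needs about 75 per arm by the normal approximation, or 84 with continuity correction.

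**6. Chance of missing the stated difference.** From 1 − 0.726 = 0.274 to 1 − 0.351 = 0.649, against the implied figure below 0.15.

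**7. What 25 women can show.** Two-sided exact (Clopper–Pearson) 95% intervals: 20/25 gives 59.3% to 93.2%; 15/25 gives 38.7% to 78.9%.

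**8. Can the composite be observed in both arms?**

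| Component | Fit2ThriveMB | Control |
|---|---|---|
| 12-week assessment completed | Yes | Yes: "At 12 weeks, the control group will participate in a virtual functional performance testing session" |
| Daily goals met on ≥ 70% of days | Yes, through the app | No: no app or step goals until after week 12 |
| Fitbit worn on ≥ 70% of days | Yes | No: Fitbit supplied after week 12 |

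Only the first component supports a comparison between arms.

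**The case against.** The best defence is that the figure came from a one-sample calculation on the total sample. Section 4.0 attaches n=50 to its calculations and names a one-sample test, and that test at n=50 gives 88.9%. This probably explains the number, but it does not rescue the sentence. The text specifies 25 per condition and contrasts intervention with control, and only about 25 women receive the intervention whose 80% rate is assumed.

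The 72.6% reading can also be challenged. It tests whether completion falls below 80%, which is not the natural meaning of the claim. Dropping it moves the chance of a miss to 38% to 65%, so the shortfall grows. It is kept here as the reading kindest to the plan.

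It is fair to say that little depends on the figure. Aim 1 is descriptive, other feasibility and safety measures are weighed before a larger trial, and the SAP disclaims conclusions about efficacy. That limits the severity, but the statement remains wrong.

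A further fair point concerns the repair. Restating power for a one-sample test would describe a test that Aim 1 does not plan. It would also need a reason for 60% as a fixed reference, which the documents do not give. A precision statement avoids both problems.

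**Conclusion.** The concern holds. The plan states power above 85%; with 25 per arm, exact power is 61.7% to 72.6% one-sample and 35.1% to 44.3% two-sample. The conclusion does not depend on which exact test was intended, and it uses only the inputs in section 4.0. It takes each woman as a success or failure and assumes all 25 in an arm are evaluable.

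Separately, the control rate for the composite cannot be observed with the data collected; only 12-week assessment completion can be compared between arms. No planned analysis uses the power figure, so enrolment and estimates are unaffected. The harm is an overstated and partly unworkable sample-size justification. It should be fixed, but it is not fatal to a pilot.

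**What to change.** In section 4.0, delete the figure above 85% and the control comparator for the composite. Then choose one of these:

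1. **Precision (preferred, because it matches the descriptive Aim 1).** Suggested text: *For a proportion in the 25 women assigned to Fit2ThriveMB, an observed 80% (20/25) has a two-sided exact 95% confidence interval of 59% to 93%; an observed 60% (15/25) has one of 39% to 79%.*
2. **Corrected power.** Suggested text: *With 25 women in Fit2ThriveMB, a one-tailed exact binomial test at 0.05 against a fixed 60% reference has about 62% power at a true rate of 80%, and reaches 85% only at a true rate of about 85%.* This needs a stated reason for the 60% and should make clear that Aim 1 itself remains descriptive.

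In Aim 1, report the proportions with exact intervals and show 12-week assessment completion in both arms descriptively.

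The sponsor should also clarify scoring. Part (a) is written as a group threshold, so it is unclear how the successful completion rate in section 4.0 relates to the two Aim 1 criteria. It is also unclear whether goal days and Fitbit-wear days are counted jointly or separately. No scoring rule or change to the feasibility rule is proposed here.

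The cost is rewording, a few exact intervals and one clarification, with no extra patients, data or tests. The stated case for n=50 becomes less favourable.
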